3.1 NEW ANALYSIS

This new analysis was added to this addendum to align with Amended Protocols 11 and 12 because it is described in the Amended Protocols 11 and 12, however removed in Amended Protocol 13.

3.1.1 Proportion of participants with a reduction from baseline in eGFR of <10%, <20%, <30%, or <40% at Weeks 24 and 48

The number and proportion of participants with a reduction from baseline in eGFR of <10%, <20%, <30%, or <40% from baseline at Weeks 24 and 48, respectively, will be summarized by treatment group. In this analysis, since by the time of final analysis, all ITT participants would have had chance to complete Week 24, but some of them may not have chance to reach Week 48 yet, those participants who do not have chance to reach Week 48 will not be included in the denominator for the reduction from baseline at Week 48. Among participants included in the denominator, if any assessments performed at Week 24 or 48, respectively, regardless of scheduled or unscheduled visit, meeting the responder criteria, then the participant will be considered as a responder; otherwise this participant will be considered as a non-responder (including participants missed the assessment at this specified week). The nominal p-value between treatment groups will be calculated by Cochran-Mantel-Haenszel method (CMH) method adjusting for screening eGFR stratification factor.

Signature Page for VV-CLIN-0636754 v1.0
act16248-16-1-9-sap-addendum

Approve & eSign

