- b After Day 1, the visits will be done every 7 days. During the active treatment period, the visit window is ±2 days for each visit. Subjects who complete the double-blind, placebo-controlled treatment period will be rolled over directly into the open-label treatment extension (see Table 2). Subjects who complete the double-blind, placebo-controlled treatment period but who will not continue with the open-label treatment extension will enter the follow-up period, which is the same for all subjects.
- c Except for complete blood count (CBC), serum and urine chemistry, and coagulation panel, laboratory tests scheduled for the early termination (ET) visit do not need to be completed if the tests were completed as part of a study visit within 4 weeks of the last visit. ET will be done 7 days ±2 days after the last study visit.
- d Follow-up days and weeks are numbered starting from the last scheduled visit in the active treatment period. Thus, for subjects who discontinue early, Follow-up Week 2 is 2 weeks after the ET visit. The visit window is ±3 days for all follow-up visits.
- e For subjects who complete the double-blind, placebo-controlled treatment period and will enter the open-label treatment extension, the Week 48 visit will serve as the baseline visit of the open-label extension.
- f Day 1 is the baseline visit.
- g See Section 5 for visit windows, and Section 5.2 for odds visit details.
- h Option for Investigator to delegate visit assessments to be performed at an alternate location, including the subject’s home, conducted by trained, qualified study personnel. During the last 6 months of the double-blind period, the subject will be trained on self-administration of the study drug and will be observed in self-administration technique.
- i Informed consent will be obtained prior to performing any study-related procedures.
- j Prior and ongoing illnesses, surgeries, use of tobacco/alcohol/recreational drugs, and allergic reactions/hypersensitivity.
- k Family history relevant to Alport syndrome and renal disease.
- l Prior medication/therapy is any medication or therapy given within 30 days before study entry (eg, before signing the informed consent form [ICF]), as well as ongoing medication or therapy.
- m Any medication taken after signing the ICF will be collected at each visit.

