- n Systolic and diastolic blood pressure measurements, pulse rate, body temperature, and respiratory rate. Vital signs collection will be performed prior to drug administration throughout the study; specifically on Day 1 and W48, vital signs will be done at 0.5 to 1 hour pre- and 4 hours post-dose.
- o Complete examination at screening, baseline, Week 24, Week 48, ET, and Follow-up Week 10. Limited (symptom-directed) examination at Weeks 12 and 36. Height should be measured at screening.
- p 24-hour urine chemistry panel (albumin, creatinine, sodium, total protein).

- q* Urinalysis: assessment of colour and appearance, and dipstick test for specific gravity, erythrocytes, pH, protein, glucose, ketones, leukocyte esterase, nitrate, bilirubin, and urobilinogen will be done locally. Microscopic examination of urine sediment, microalbuminuria, urine creatinine, and urine protein will be a laboratory test.
- r* Full hematology panel performed weekly during treatment period and at each visit timepoint during the follow up period: hemoglobin, hematocrit, red blood cell (RBC) count, white blood cell (WBC) count with differential, and platelet count.
- s* Coagulation panel: prothrombin time, activated partial thromboplastin time (aPTT), international normalized ratio (INR), and fibrinogen.
- t* Total protein, glucose, Cystatin C, creatinine for calculation of estimated glomerular filtration rate (eGFR), uric acid, lactate dehydrogenase, sodium, potassium, chloride, bicarbonate, calcium, iron, phosphate, blood urea nitrogen (BUN), and hepatic function panel (albumin, total bilirubin, direct bilirubin, alanine aminotransferase [ALT], aspartate aminotransferase [AST], alkaline phosphatase [ALP], and gamma-glutamyl transferase [GGT]). In the event of elevated aminotransferases (ALT or AST) >3 xULN, see [Section 10.3.2](#) for guidance on additional monitoring. If subject experienced low protein <1 g the investigation will be done by the Investigator as per local practice. In case of worsening of eGFR, the Investigator could repeat the eGFR before the next scheduled test.
- u* Total cholesterol, triglycerides, high-density lipoprotein (HDL), and low-density lipoprotein (LDL).
- v* For women of child bearing potential, a blood pregnancy and a monthly urine pregnancy test will be performed; in case the urine test is positive, injections will be stopped and a blood test will be performed to confirm the pregnancy.

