- ff* Genotyping is not needed for randomization except for patient for whom historical data for genetic confirmation of Alport syndrome and a kidney biopsy showing glomerular basement membrane abnormalities consistent with Alport Syndrome are not available at screening visit.
- gg* Day 1 should be within 3 calendar days maximum after assignment to treatment group.
- hh* Please refer to [Section 6.2.9](#).
- ii* Markers of inflammation: quantitative immunoglobulin (γ -globulin, IgG, IgM).
- jj* At unscheduled visits, only blood samples that are needed for abnormal laboratory value follow up will be collected. ECGs will only be performed in case an abnormality potentially has an impact on the continuity of the study drug administration, as deemed by the Investigator.
- kk* The USVs may be done at alternative location visit (as described in footnote [h](#)), except when abnormal safety parameters are linked to physical examination.

Table 2 - Schedule of events for open-label treatment extension period and follow-up period

	Open-Label Treatment Extension Period ^a																								USV ^{aa}	ET ^b	Follow-up ^c				
STUDY WEEK	48	49	50	52	54	56	58	60	62	64	66	68	70	72	74	76	78	80	82	84	86	88	90	92	94	96			2	4	10
STUDY DAY	337	344	351	365	379	393	407	421	435	449	463	477	491	505	519	533	547	561	575	589	603	617	631	645	659	673			15	29	71
Site Visits ^d	X	X	X	X	X	X	X	X	X	X	X	X	X	X	X	X	X	X	X	X	X	X	X	X	X	X	X	X	X	X	X
Alt. location option ^e		X	X		X	X	X		X	X	X	X	X		X	X	X	X	X		X	X	X	X	X		X ^{bb}		X	X	
Concomitant medications	X			X		X		X		X		X		X		X		X		X		X		X		X	X	X			X
Vital signs ^f and body weight	X			X				X					X						X							X	X	X			X
Physical examination ^g	X							X					X						X							X	X	X			X
12-lead ECG ^v	X							X					X						X							X	X	X			
Hearing Assessment	X																									X		X			
Spot urine protein-to-creatinine ratio (UPCR)	X			X		X				X		X				X		X				X		X							
Subject collects 24-hour urine sample prior to visit ^h	X							X					X						X							X	X	X			
Urinalysis ⁱ	X			X				X					X						X							X	X	X			X
CBC ^w	X	X	X	X	X	X	X	X	X	X	X	X	X	X	X	X	X	X	X	X	X	X	X	X	X	X	X	X	X	X	X
Coagulation panel ⁱ	X			X		X		X		X		X		X		X		X		X		X		X		X	X	X			X
Serum chemistry ^{k, n}	X			X		X		X		X		X		X		X		X		X		X		X		X	X	X			X
Lipid panel ^l , hs-CRP	X			X				X					X						X							X	X	X			X
Blood pregnancy ^m	X																														

	Open-Label Treatment Extension Period ^a																								USV ^{aa}	ET ^b	Follow-up ^c				

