In case of worsening of eGFR (that do not reach stopping criteria) or UPCR, the Investigator or the Sponsor could repeat the test before the next scheduled one as often as medically needed. The Sponsor needs to be consulted before a decision to discontinue the patient, unless it is a case of emergency.

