5.6 UNSCHEDULED VISITS

Unscheduled visits are those visits that occur beyond regularly scheduled visits and are performed in order to assess a previously noted AE (especially if the AE is considered by the Investigator to be possibly related to the use of study drug), abnormal/alarming laboratory values, and/or clinical findings. In such cases, the Investigator may at his/her discretion arrange for a subject to have an unscheduled visit. The subject will be contacted to arrange an unscheduled visit to assess the noticed abnormalities. **Only focused assessments (guided by the reason for the visit) are foreseen for these visits**, and there will be no need to collect very extensive additional laboratory or other safety and efficacy data.

The unscheduled visits could be done at alternative location (including at home), and at the Investigator's discretion, for the assessment of AEs related to abnormal/alarming laboratory values.

The Unscheduled Visit Page in the eCRF must be completed ([Table 1](#), [Table 2](#)).

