4 STATISTICAL ANALYSES

4.1 GENERAL CONSIDERATIONS

For the analyses for the primary, secondary and tertiary/exploratory objectives, the corresponding analyses population are summarized in [Table 2](#) and [Table 5](#), and the analyses period is on the double blind placebo-controlled period.

However, the analyses for placebo controlled and open label treatment period combined are discussed in [Section 4.8.5](#).

Observation period

The observation period will be divided into the following segments:

The **pre-treatment period** is defined as the time from the signed informed consent (and ascent for adolescent in Stage 2) date up to the first administration of the IMP.

For the **placebo-controlled treatment period**, the treatment-emergent (TE) period is defined as the period from the first IMP administration to

- the first administration of the IMP in open-label extension period for participants who entered open-label extension period or,
- the last administration of the IMP + 7 days if the participant is ongoing or not continuing in open-label treatment extension period (eg, early discontinuation of treatment).

For the **lademirsen treatment period**, the TE period is defined as the period from the first lademirsen administration the last administration of lademirsen + 7 days. The period is defined for participants who had at least 1 full or partial administration of lademirsen.

For the **overall study period**, the TE period is defined as from the first IMP administration to the last administration of the IMP + 7 days.

For the **post-treatment period**, it is defined as the period from the end of overall study TE period until the end of the study (eg, the later day of the last scheduled visit, or the end-of-study date collected on e-CRF page “Completion of End of Study/Follow-up”. If death is the end-of-study reason, date of death will be used.)

The TE period and on-treatment period are defined the same, therefore, the wording may be used interchangeably.

The lademirsen treatment period and overall study period are used for analysis in [Section 4.8.5](#).

In general, for analysis in the **placebo-controlled treatment period**, the baseline is the last available value prior to first IMP. For analysis in the **lademirsen treatment period**, the baseline is the last available value prior to the first administration of lademirsen.

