5.3 APPENDIX 3 DATA HANDLING CONVENTIONS

For analyses of all the primary, secondary and exploratory endpoints during placebo-controlled treatment period, with the exception for the endpoints only collected at Stage 2, data from both Stage 1 and Stage 2 data will be included for the analyses.

Derivation of "year" for eGFR slope analysis

Year of each eGFR measurement relative to the first IMP injection is calculated as (date of eGFR measurement - the first IMP injection date +1) divided by 365.25. Specially, for the last non-missing eGFR measure collected prior to first IMP injection, it will be coded to year=0.

Missing data handling for eGFR

The primary analysis will include all data collected in Primary Population, regardless of whether or not subjects completed the treatment period. Subjects who prematurely and permanently discontinue study medication will be requested to enter 10 weeks post-treatment follow up period. Data collected during those 10 weeks post-treatment period will be included in the primary analysis up to 48 weeks for Stage 1 data, and up to 96 weeks for Stage 2 data.

All efforts will be made to minimize the amount of missing data. eGFR data is scheduled to be collected at baseline, Week 2, Week 4, and every 4 weeks thereafter. However, if data was not collected at the scheduled visits, every possible effort should be made to collect the data at next possible unscheduled visits, and a corresponding week will also be assigned for those unscheduled visits for analysis purpose. For example, if a subject cannot come for a scheduled visit at Week 16, then an unscheduled visit between Week 16 and Week 20 should be planned, and if this unscheduled visit happens on Week 18, then Week 18 data will be used for the analysis.

Demographic formulas

Age at diagnosis of Alport syndrome is calculated as:

$$(\text{Date of diagnosis of Alport syndrome [yyyy-mm-dd]} - \text{Date of informed consent or assent for adolescent [yyyy-mm-dd]})/365.25 + \text{Age at informed consent or assent for adolescent}$$

Time from diagnosis of Alport syndrome (years) is calculated as:

$$(\text{Date of randomization [yyyy-mm-dd]} - \text{Date of diagnosis of Alport syndrome [yyyy-mm-dd]})/365.25$$

For the dates used in the above calculations, if month is missing, it will be imputed to June; and if the day is missing, it will be imputed to the 15th.

Handling of missing data for categorical variable

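### The eGFR responder rule in SAP addendum 3.1.1 takes the best value at Week 24 or 48, so unscheduled repeats can only add responders; a minor, cheaply fixed point, chiefly at Week 24

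*SAP*

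**What the plan says.** A responder in addendum 3.1.1 has lost less than 10, 20, 30 or 40% of baseline eGFR at Week 24 or Week 48. An assessment at that week counts "regardless of scheduled or unscheduled visit, meeting the responder criteria, then the participant will be considered as a responder". Anyone else, including a participant with no assessment at the week, is a non-responder. The arms are compared by a CMH test stratified by screening eGFR, with a nominal p-value.

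Other provisions bear on which values exist and which count:

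- **Repeats.** Protocol Table 1, footnote t: "In case of worsening of eGFR, the Investigator could repeat the eGFR before the next scheduled test". Protocol 3.3.1.1 says the investigator or sponsor "could repeat the test before the next scheduled one as often as medically needed".
- **Unscheduled visits.** Protocol 5.6 describes visits "performed in order to assess a previously noted AE", or to follow abnormal laboratory values or clinical findings. Table 1, footnote jj: "At unscheduled visits, only blood samples that are needed for abnormal laboratory value follow up will be collected".
- **Make-up visits.** SAP 5.3 asks for a missed eGFR to be collected at an unscheduled visit and assigns that visit a week. In its Week 16 example, "if this unscheduled visit happens on Week 18, then Week 18 data will be used for the analysis". No day limits are given.
- **General convention.** SAP 5.3 also keeps unscheduled laboratory values out of by-visit summaries unless they are re-allocated to a scheduled visit.
- **Analysis period.** SAP 4.1: "the analyses period is on the double blind placebo-controlled period". That period ends at the first open-label dose, or 7 days after the last dose for those who do not continue.

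**The concern.** An any-value rule is harmless if extra measurements arise independently of the result. Here most of them do not. The discretionary repeat is provided for worsening, without a cap, and a participant whose scheduled value already qualifies has no comparable reason to be re-tested. The extra chances to qualify go mainly to participants who have just failed.

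The addendum also sets aside the SAP's general treatment of unscheduled laboratory values without saying so. It gives no day window for a value to count as belonging to the week, so two programmers could include different repeats.

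At stake is the level of the reported responder proportions. With 43 participants at 2:1 there are 43/3 = 14.3 on placebo, and one reclassified placebo participant moves the proportion by 1/14.3 = 7.0 points.

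**Working it through.** **Direction (exact).** Let S be the event that the scheduled value qualifies and U the event that some unscheduled value in the week qualifies. The addendum's responder set is S or U, which contains S. When the scheduled value is missing, both the addendum's rule and a scheduled-first rule with the same window rely on the unscheduled value. So no one moves from responder to non-responder. A participant whose true value lies at a cut-off qualifies with probability 0.5 on one value, 1 − 0.5² = 0.75 on two and 1 − 0.5³ = 0.875 on three, given independent errors.

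**Size (illustrative).** The documents give no figure to reproduce for this endpoint, and the residual and slope SDs are redacted.

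- From the documents: slopes of −10 (placebo) and −5 (planned effect) mL/min/1.73 m²/year (Protocol 7.2.1); 43 participants at 2:1 (SAP 1.1).
- Assumed: true baseline b = 50, 60 or 75; (slope SD, residual SD) = (4,3), (4,4), (6,4) or (6,6); one same-week repeat with probability p once the observed loss reaches a trigger of 10, 20 or 30%.

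Observed baseline = b + e₀. Week 24 value = b + slope × 24/52.18 + e₁. The repeat has the same true value and a new error e₂. For cut-off c:

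gain = p × Pr(first loss ≥ c and ≥ trigger, second loss < c).

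With 1,000,000 simulated participants per arm and cell, b = 60 and p = 0.5, the placebo gains in percentage points over the four SD pairs are:

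| Repeat triggered at a loss of | <10% cut-off | <20% | <30% |
|---|---|---|---|
| ≥10% | 7.5–8.2 | 1.6–5.5 | 0.0–1.8 |
| ≥20% | 0.4–2.5 | 1.6–5.5 | 0.0–1.8 |
| ≥30% | 0.0–0.4 | 0.0–1.1 | 0.0–1.8 |

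One cell in full (b = 60, SDs 4 and 4, trigger 10%, p = 0.5, <10% cut-off): placebo 59.7 → 67.7, lademirsen 74.3 → 80.9, difference 14.6 → 13.2.

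The 30% trigger is where an eGFR fall becomes an adverse event of special interest (Protocol 6.2.2 and Table 3). At that trigger the largest gain over b = 50–75 at p = 0.5 is 3.4 points (b = 50, residual SD 6, <30% cut-off).

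**What p = 0.5 requires.** Suppose every loss of 10% or more is repeated at a uniformly random time in the 28 days before the next test. The share falling in the week is then 2/28 = 7%, 7/28 = 25% or 14/28 = 50% for windows of 2, 7 or 14 days. The p = 1 gain for the <10% cut-off at b = 60 is 15.0–16.3 points, so:

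- 2 days: 15.0 × 2/28 to 16.3 × 2/28 = 1.1–1.2 points;
- 7 days: 3.7–4.1 points;
- 14 days: 7.5–8.1 points.

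In placebo participants, 1.2 points is 14.3 × 0.012 = 0.17, 3.4 points is 0.49, and 8.2 points is 1.2.

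**Arm difference at Week 24.** Over all cells the change is 0 to about −2.5 points at p = 0.5 and 0 to about −5 at p = 1.

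**The case against.** The strongest reply is that 3.1.1 is a complete, prespecified rule. Given a set of Week 24 values, it returns one answer. That stands: a reader might infer that the plan has no rule for multiple values, but it has one. What it lacks is the boundary of the week, and the rule it chose is the one most open to selective re-testing.

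Second, the effect may be close to nil. Repeats are discretionary, and a fall of 10 to <30% is not an adverse event of special interest. Chemistry is normally central (Table 1, footnote w), so a repeat prompted by a result must wait for that result. Under footnote b, "After Day 1, the visits will be done every 7 days", so Week 25 is a natural slot. This also stands. A reader might take the 8-point figure as the expected inflation. It is not: under the timing model above it needs every loss of 10% or more repeated and a 14-day window.

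Third, not every unscheduled creatinine follows worsening. Make-up visits are legitimate, and the work-up for raised ALT or AST (Protocol 10.3.2) includes serum creatinine. The claim is therefore that repeats mainly follow worsening, and the documents do not quantify it.

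Fourth, a reader might infer that the rule favours lademirsen, or that open-label values enter Week 48. Neither is supported. At Week 24 the simulated difference never widened. At Week 48, continuing participants receive the first open-label dose at that visit (Protocol 5.3), which closes the period. Others are limited to last dose plus 7 days (SAP 4.1), and addendum section 3 restricts efficacy to Week 48. The statement about the arm difference covers Week 24 only: with unrestricted Week 48 repeats at p = 1, some <10% cells widened by up to 3.4 points, but these period limits exclude most such repeats.

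**Conclusion.** The point holds as a minor one. That the rule can only add responders relative to the scheduled value follows from the rule itself. That the additions fall mainly on participants who had worsened follows from the protocol's repeat provisions.

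The size is not determinable. It depends on redacted SDs, an unknown repeat frequency and trigger, and an unstated window, and it is zero if no repeat falls in the week. Under the assumptions shown, the placebo gain at Week 24 is about 1 point for the <10% cut-off with a 2-day window. With repeats only at losses of 30% or more it is 0 to 3.4 points at p = 0.5 for any cut-off. About 8 points arises only in the demanding p = 0.5 case at a 10% trigger. Week 48 exposure is small.

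No decision turns on this. It concerns one secondary endpoint with a nominal p-value and no multiplicity adjustment, in a trial already stopped for futility.

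**What to change.** Before the final database lock, amend addendum 3.1.1 to:

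- use one value per participant and week, the scheduled-visit eGFR;
- use an unscheduled value only when the scheduled one is missing, within a stated day window consistent with the week-assignment and unscheduled-visit conventions in SAP 5.3, and say whether a make-up value counts for the missed week;
- cross-refer to SAP 4.1 so that Week 48 uses only values before the first open-label dose;
- keep missing as non-response;
- report the any-value rule only as a sensitivity analysis.

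The cost is a short paragraph and a small change to the derivation. No new data are needed. Responder rates may be slightly lower in both arms.
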